The specific reasons for not using an anticoagulant in eligible AF patients are poorly defined. The AVERROES trial provided some insight into reasons for patients deemed "unsuitable for warfarin" with 42% unable to maintain therapeutic INR, 43% unlikely to monitor INR, and 37% refusing warfarin. The reasons for underuse of oral anticoagulation are likely related to three types of barriers: patient-level barriers (i.e. overestimation of risk of bleeding, underestimation of risk of stroke, misperceptions of adverse events from OACs), provider-level barriers (i.e. overestimation of risk of bleeding, underestimation of risk of stroke, misperceptions of adverse events from OACs, misperceptions about a patient's fall risk, misperceptions of the benefits of aspirin in stroke prevention), and system-level barriers (i.e. lack of time in a clinic visit to discuss stroke prevention, access to care such as an anticoagulation clinic, cost of OACs, feasibility of warfarin monitoring).

Another issue driving under-treatment with oral anticoagulants is poor medication adherence, which may be driven by patient barriers or system-level barriers. Medication non-adherence is defined as a patient's passive failure to follow a prescribed drug regimen. An average of 50% of patients are non-adherent to their prescribed treatment regimens for chronic diseases, such as AF.³² Non-adherence rates are similar across disease states, treatment regimens, and age groups, with the first several months of therapy characterized by the highest rates of discontinuation.³³ Interventions to support patient management of medications have fallen short, and sustainable adherence rates have not improved.^{34,35}

The cost to the health care system of hospitalizations due to medication non-adherence for all disease states may be as high as approximately \$100 billion annually. Patient-provider communication regarding medication use is poor, and opportunities to document and provide feedback on metrics for medication adherence are not readily available in EMR applications. Meaningful and measurable improvements in adherence require a comprehensive, multifaceted intervention in which all participants, including physicians, play an active part.

III. RESEARCH HYPOTHESIS

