- 5. Proportion of patients actively on OAC at 12 months of follow-up
- 6. Incident rate of hospitalization for any bleeding
- 7. All-cause in-hospital mortality rates
- 8. All-cause mortality rates among patients with accurate out-of-hospital mortality data (such as Medicare Advantage patients)
- 9. Health care utilization for AF patients, which would be reported as counts of number of health care utilization events (outpatient visits, days hospitalized, number of emergency department visits, etc.)

C. EXPLORATORY OBJECTIVES

The exploratory objectives are to:

- 1. Evaluate the effect of the early and delayed education interventions on primary and secondary endpoints over the course of the follow-up through the date on which at least 80% of eligible study participants have at least 24 months of follow-up time.
- 2. Explore the CTTI and the FDA supported Sentinel Data Partnership's ability to successfully conduct a pragmatic trial to answer important questions to improve public health.

VI. STUDY DESIGN AND DURATION

The study is a prospective, randomized, and open-label education intervention trial. Patients with AF and a CHA₂DS₂-VASc score of 2 or greater will be randomized in a 1:1 ratio to an early intervention cohort and a delayed intervention cohort within each participating health plan. The definition for OAC medication fill will be an OAC medication dispensing or at least 4 INR tests in the claims data.¹ The claims records of the patients randomized to the early intervention cohort will then be linked to "fresh" (i.e. about 1-4 months old) pharmacy claims data at the time of randomization. Patients without evidence of an OAC medication fill during the 12 months prior to randomization will be included in the patient-level and provider-level early educational intervention (patients randomized to this early intervention with evidence of an OAC medication fill during the 12 months prior to randomization will be excluded from the trial.). In addition to usual care, these patients and their providers² will receive a

¹Not all OAC dispensings are well captured in pharmacy claims, particularly, for warfarin. INR tests are assumed indicative of OAC fills that were not billed through the claims. 4 INR tests or values within a 12-month period will be used as a proxy since that is roughly the number of tests administered in the process of stabilizing dose.

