- 2. Time to OAC start: the time to first OAC initiation, as defined by the first fill date for apixaban, dabigatran, edoxaban, rivaroxaban, or warfarin. If there was no prescription fill for these medications, but the patient had 4 or more INR values measured over the study period, the date of the first INR measurement will be used for initiation of OAC.
- 3. OAC prescription coverage: the proportion of days that AF patients have OAC prescription fills over the duration of the study. The assumption is that a 30-day or 90-day supply will last for the planned period, even in the case of warfarin, when the length of time that a prescription lasts may be less well defined. Patients will only be included in this secondary analysis, if they had a prescription fill for apixaban, dabigatran, edoxaban, rivaroxaban, or warfarin.
- 4. OAC rates at follow-up: proportion of patients with an active oral anticoagulant dispensing at the end of the one-year follow-up. This will include patients with apixaban, dabigatran, edoxaban, rivaroxaban, or warfarin medication fills that encompass the end of the study period. If there was no prescription fill for these medications, this will also include patients with 4 or

more INR values measured over the study period, who had an INR value measured within 60 days of the end of the approximately one-year follow-up.

- 5. Rate of stroke or TIA: the incident rate of stroke or TIA related hospitalizations; stroke, excluding transient ischemic attacks (TIAs), will also be assessed
- 6. Rate of bleeding related hospitalization: the incident rate of hospitalizations for any bleeding
- 7. Health care utilization: the total counts of health care utilization (number of outpatient visits, emergency department visits, hospital admissions, etc.) for AF patients, including AF and non-AF related care
- 8. In-patient all-cause mortality: patients with in-hospital death
- 9. All-cause mortality: in a subset of patients with mortality status

XVI. STATISTICAL ANALYSES

A. DEMOGRAPHICS AND BASELINE CHARACTERISTICS

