1. 33% OAC initiation rate in the delayed intervention arm
2. 38% OAC initiation rate in the early intervention arm (5% absolute improvement in OAC initiation over the 33% OAC initiation expected in the delayed intervention arm over 1-year follow-up)
3. 1-year attrition rate: 30% dropout or lost-to-follow-up
4. Two-sided type I error rate of 0.05
5. Roughly 10,000 patients who meet the inclusion/exclusion criteria will yield more than 99% power to detect a 5% absolute difference

Power	Total sample size (2-arm)	Early Intervention	Delayed Intervention
90%	5610	2805	2805
95%	6910	3455	3455
99%	9718	4859	4859

2. Important Secondary Outcome of Stroke or TIA

A study with approximately 80,000 patients could provide reasonable power for stroke or TIA outcome under certain assumptions listed below:

- 1-year stroke or TIA rate: 18% among patients not treated with OAC
- 1-year stroke or TIA rate: 7% among patients treated with at least 1 OAC fill
- Duration of follow-up: 1 year
- 33% of delayed intervention patients will have at least 1 fill of OAC, meaning the 1-year stroke or TIA rate in the delayed intervention group would be 14.4%
- 1-year attrition rate: 30% dropout or lost-to-follow-up
- Two-sided type I error of 0.05
- If 38% of early intervention patients have at least 1 fill of OAC (meaning the 1-year stroke or TIA rate in the early intervention group would be 13.82%, i.e., an absolute reduction of 0.55%), the study will have 46% power to detect this 0.55% reduction. However, if 40.5% of early intervention patients have at least 1 fill of OAC (meaning the 1-year stroke or TIA rate in the

early intervention group would be 13.54%, i.e., an absolute reduction of 0.83%), the study will have 80% power to detect this 0.83% reduction.

8. The sample size has 80% power to detect a 0.5% absolute reduction in stroke, assuming a cumulative 1-year incidence of stroke of 4.2% in control (delayed intervention arm) patients and 3.7% in intervention (early intervention arm) patients. The assumption is that patients not on oral anticoagulation have an annual stroke rate of 5%, and stroke will be reduced by 50% (HR=0.5) in the treated (anticoagulated) population. The 80% power requires that 52% of early intervention arm patients are treated at 1-year as compared to 33% in the control arm.

II. STATISTICAL ANALYSIS

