The proportion of patients actively on OAC at the end of follow-up will be summarized and compared between the early intervention and delayed intervention arms. Last Observation Carried Forward will be used if the patient is censored. To evaluate whether the early patient-level and provider-level educational intervention increases the proportion of patients being actively on OAC at the end of follow-up, we will calculate the odds ratio (i.e., the odds of an average patient in the early intervention group being actively on OAC at the end of follow-up as compared to the odds of an average patient in the delayed intervention group being actively on OAC at the end of follow-up) using logistic regression model adjusted for baseline risk factors listed in Appendix A Table A, with GEE to account for the correlation of responses among the patients from a same service provider. The odds ratio, 95% confidence interval (CI) and p-value will be presented to show whether there is a statistically significant difference in the proportion of patients who are actively on OAC at the end of follow-up between the early intervention and delayed intervention groups. Each Data Partner will run the SAS program(s) distributed by HPHCI, developed with the statistical team at Duke DCC, to perform logistic regression analysis on their cohort of patients and return the parameter estimate (SE), estimated odds ratio, 95% confidence interval (CI) and p-value, shown in Table 6 in Appendix A (there will be one for each Data Partner), to HPHCI. Meta-analysis methods with inverse-variance weighting on log scale will be used to integrate the results and obtain the estimate of the overall odds ratio, 95% confidence interval and p-value for entire study population.

4. Clinical Outcomes

Claims data (ICD-10-CM codes used for defining these outcomes are listed in Appendix C) will be used to define the following clinical outcomes:

- Hospitalization for ischemic stroke or unknown stroke
- Hospitalization for TIA
- Hospitalization for systemic embolism
- Hospitalization for ischemic stroke, TIA or systemic embolism
- Hospitalization for hemorrhagic stroke
- Hospitalization for any bleeding
- Hospitalization for ischemic or hemorrhagic stroke
- Hospitalization for ischemic or hemorrhagic stroke or systemic embolism
- Composite of ischemic stroke, hemorrhagic stroke, and hospitalization for any bleeding
- All-cause in-hospital death

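### Last observation carried forward for the active-on-OAC endpoint replaces 12-month status with status at a variable censoring date, and the resulting bias can go either way

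*SAP*

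**What the plan says.** - **Time point.** Protocol V.B lists the endpoint as "Proportion of patients actively on OAC at 12 months of follow-up", and SAP I.B lists it in the same terms. Protocol XV, item 4, defines it as the "proportion of patients with an active oral anticoagulant dispensing at the end of the one-year follow-up".
- **Analysis.** SAP II.D.3 moves the time point to the end of follow-up. It compares the arms by an adjusted odds ratio with a p-value, read as "the odds of an average patient in the early intervention group being actively on OAC at the end of follow-up" against the same odds in the delayed group.
- **Censored patients.** The only rule is "Last Observation Carried Forward will be used if the patient is censored". The SAP gives no reason for it, does not define the last observation, and plans no sensitivity analysis for this endpoint. The as-randomized sensitivity analysis in SAP II covers the primary endpoint only.
- **Denominator.** SAP II.D.3 reads as all patients in each arm. The shell of Table 6 in Appendix A limits the endpoint to patients with at least one day of OAC.
- **Attrition.** SAP I.G assumes "1-year attrition rate: 30% dropout or lost-to-follow-up". SAP II allows that loss to follow-up may differ between the arms.
- **Reasons for censoring.** Protocol XIV.B lists death, leaving the plan, loss of medical or pharmacy coverage, and loss of research eligibility.

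**The concern.** The endpoint asks who is on OAC at one fixed date. The rule answers with status on whatever date each censored patient was last seen. All analysed patients start off OAC, so the rule makes two kinds of error. A patient censored before a first fill is frozen as off, although some would have started by month 12. A patient censored while on treatment is frozen as on, although some would have stopped, and one who died on treatment stays on.

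These errors cancel between arms only if the arms share the same time course and the same attrition. Otherwise the reported odds ratio and p-value mix earlier differences, or differences in attrition, into a result labelled as 12-month OAC use. SAP II tests at 0.05 with no multiplicity adjustment, so a false signal here could be read as an effect on sustained use.

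**Working it through.** **Inputs from the documents.** "33% OAC initiation rate in the delayed intervention arm"; "38% OAC initiation rate in the early intervention arm"; 30% attrition (SAP I.G); 80,000 patients, 1:1, so 40,000 per arm (Protocol XIV.A).

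**Is 30% the plan's working figure?** Yes. For 33% vs 38%, two-sided 0.05, the continuity-corrected formula gives 1963, 2418 and 3401 per arm at 90%, 95% and 99% power. Dividing by 0.70 and rounding up gives 2805, 3455 and 4859, or totals of 5610, 6910 and 9718. These match the sample-size table exactly.

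**Assumptions, because the documents give no values.** A share of 0-50% of starters stop within 12 months of starting (Weibull shape 1.0 or 0.6), with no restarts. Censoring is exponential and unrelated to OAC status. The last observation is status on the censoring date. The target is status at day 365.

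**Check by hand: no stopping, constant start hazard.** With yearly start hazard h and censoring hazard c, the carried-forward share is h/(h+c) × [1 − exp(−(h+c))].
- Delayed arm: h = −ln 0.67 = 0.400, c = −ln 0.70 = 0.357. The share is 0.529 × (1 − 0.67 × 0.70) = 28.1%, against a target of 33%.
- Early arm: h = −ln 0.62 = 0.478. The share is 0.573 × (1 − 0.62 × 0.70) = 32.4%, against a target of 38%.
- The difference falls from 5.0 to 4.3 points, and the odds ratio from 1.244 to 1.228.

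**All settings, 30% attrition in both arms, all patients in the denominator.**

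| Time course of the effect | Target at day 365 | Carried forward |
|---|---|---|
| Steady relative effect | OR 1.195-1.244; 3.13-5.00 points | OR 1.191-1.228; 2.79-4.33 points |
| +5 points within 60-90 days, then kept | OR 1.154-1.244 | OR 1.184-1.258 |
| +5 points within 60 days, faded by day 365 | −1.15 to 0.00 points | −0.27 to +0.78 points |

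- Second row: the odds ratio rises by 0.01-0.03. An example is 1.158 to 1.185 (gain over 90 days, 50% stopping, shape 1.0). The risk difference moves by only −0.22 to +0.23 points.
- Third row: the difference is overstated by 0.74-0.88 points. The +0.78 is the case with no stopping, where the true difference is zero. A rough check: the gap averages 2.5 points over the year and 30% of patients are censored, so 0.30 × 2.5 = 0.75. At 40,000 per arm the standard error is √(2 × 0.285 × 0.715 / 40,000) = 0.32 points. Then z = 2.44, and the false difference is significant about 68% of the time.

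**Which error is larger?** With 35% stopping (shape 0.6):
- Delayed arm: 4.0% frozen off but on at month 12, and 0.5% frozen on but off. The level is 25.1 + 0.5 − 4.0 = 21.6%.
- Early arm (gain within 60 days): 4.1% and 0.7%. The level is 28.4 + 0.7 − 4.1 = 25.0%.

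Freezing before starting dominates and lowers both levels. In Table 6's denominator of starters only, freezing before stopping dominates. With 50% stopping (shape 1.0, gain within 60 days), the active share rises from 68.2% to 70.4% (early) and from 70.6% to 72.3% (delayed). The difference shrinks from −2.31 to −1.93 points.

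**Unequal attrition, no true effect.** With 35% stopping (shape 0.6), attrition of 25% vs 30% gives a false 0.61 points (OR 1.036) in favour of the arm that loses fewer patients. The standard error is √(2 × 0.219 × 0.781 / 40,000) = 0.29 points. Then z = 2.09, significant about 55% of the time. With no stopping, the formula above with c = −ln 0.75 = 0.288 gives 28.9% vs 28.1%, or 0.87 points.

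**The case against.** The strongest defence has four parts.

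1. This is one secondary endpoint among several, and the primary analysis does not use the rule. That stands.
2. With equal attrition the distortion is small unless the effect fades, and with no effect at any time it is zero. That also stands, but the SAP itself doubts that loss will be equal.
3. If the end of follow-up means each patient's own last day, carrying forward is simply the definition. Then the endpoint is not the 12-month status that Protocol V.B, Protocol XV and SAP I.B name, so the passages still conflict.
4. Carrying forward keeps every patient, while an analysis of those still covered can be biased if leaving relates to OAC use. This is a fair reason for weights and a sensitivity analysis. In the model above, completers recover the target only because censoring was assumed unrelated to OAC status.

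A reader might infer something stronger: that the rule freezes patients before they stop and so favours a one-time letter that acts early. The documents do not support this. They give no time course for the effect; a single mailing and the 42-, 90- and 183-day windows of Table 2b do not supply one. The remark in Protocol II about "the first several months of therapy characterized by the highest rates of discontinuation" concerns chronic-disease treatment in general and gives no OAC stopping rate. With all patients in the denominator, the larger error is freezing before starting, and under a steady relative effect the rule understates.

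**Conclusion.** The concern holds in a direction-neutral form. The plan's only handling of censored patients substitutes status at a variable date for 12-month status in up to 30% of patients, and it can count deaths as active. The effect on the arm contrast ranges from slight understatement, through an odds-ratio overstatement of 0.01-0.03, to a false 0.7 to 0.8 points when an early gain has fully faded. A 5-point gap in attrition alone creates about 0.6 points, as large a problem as most of the timing effects.

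These sizes are illustrative. They rest on assumed stopping of 0-50%, assumed time courses, censoring unrelated to OAC use, and 40,000 analysed per arm. The size in the reported table cannot be fixed until the time point and denominator are settled. The change should be made, but it does not bear on the trial's main conclusion.

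**What to change.** - Assess status at day 365 in patients still enrolled with pharmacy coverage on that day. Weight them by the inverse probability of remaining enrolled, using the Table A covariates, fitted by arm within each Data Partner.
- State how death is handled, for example as not active, or through a while-alive estimand. Weighting survivors up to stand for the dead should not happen by default.
- Use one time point and one denominator across SAP I.B, SAP II.D.3 and Table 6. A comparison among starters only conditions on an outcome of the intervention, so it should be labelled descriptive if kept.
- Report censoring by arm and reason.
- Keep the present rule as a sensitivity analysis, with the last observation defined.

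**Cost.** One weight model per Data Partner. Standard errors rise by about 20% from the smaller sample (1/√0.70 = 1.20), plus whatever the spread of the weights adds. At 28,000 per arm the standard error of the difference is about √(2 × 0.267 × 0.733 / 28,000) = 0.37 points, which is affordable against differences of about 3 points.
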